9.4 Efficacy Analyses

9.4.1 Primary Endpoint Analyses

A Mixed Model Repeated Measures (MMRM) analysis will test whether AGT shows greater improvement in SIGH-D-17 at Week 8 than TAU. Formally, the analysis tests for a difference in mean change from baseline to Week 8 between the treatment groups, in the FAS population. Compared to analyzing All Randomized subjects, this excludes subjects who don't return after the Baseline Visit, which is generally acceptable if this excluded group is small.

In the MMRM model, the dependent variable is the change in SIGH-D-17 from baseline at each of the scheduled visits Week 2, Week 4, Week 6 and Week 8. The model will include the fixed effect continuous factor baseline SIGH-D-17, and fixed effect categorical factors (pooled) investigative site, treatment group (AGT and TAU; 2 levels), visit (Weeks 2, 4, 6 and 8; 4 levels), and treatment x visit interaction. The interaction term will remain in the model regardless of statistical significance. An unstructured covariance pattern will be used to estimate the variance-covariance matrix of the within-subject repeated measures (i.e., model within-subject errors). The variance-covariance matrix will be estimated across both treatment arms. The fixed effects will be estimated by the method of restricted maximum likelihood estimation using the Newton-Raphson algorithm, based on all available data. The denominator degrees of freedom and adjustment of standard errors will use the Kenward-Roger method.

AGT and TAU mean change in SIGH-D-17 at Week 8 will be estimated and tested utilizing the least squares (LS) means from the treatment x visit interaction in the MMRM model. The primary analysis

will test the difference (contrast) between the Week 8 LS means, at two-sided significance 0.05. The test p-value and the 95% CI for the difference in Week 8 means will be presented. Comparisons between the AGT and TAU means at Week 2, Week 4 and Week 6 will also be generated. Diagnostics for outliers, non-normality and other model assumptions will be run. Significant findings will be followed up with appropriate sensitivity analyses.

To allow comparison with previous SIGH-D-17 studies, two supportive analyses of the primary endpoint will be produced. Each will be an Analysis of Covariance (ANCOVA):

- 1) Last Observation Carried Forward (LOCF) analysis, and
- 2) Observed Cases (OC) analysis.

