#### Primary Endpoint Analyses

A Mixed Model Repeated Measures (MMRM) analysis will test whether AGT shows greater improvement in SIGH-D-17 at Week 8 than TAU. Formally, the analysis tests for a difference in mean change from baseline to Week 8 between the treatment groups, in the FAS population. Compared to analyzing All Randomized subjects, this excludes subjects who don't return after the Baseline Visit, which is generally acceptable, if this excluded group is small. In the MMRM model, the dependent variable is the change in SIGH-D-17 from baseline at each of the scheduled visits Week 2, Week 4, Week 6 and Week 8. The model will include the fixed effect continuous factor baseline SIGH-D-17, and fixed effect categorical factors investigative site, treatment group (AGT and TAU; 2 levels), visit (Weeks 2, 4, 6 and 8; 4 levels), and treatment x visit interaction. The interaction term will remain in the model regardless of statistical significance. An unstructured covariance pattern will be used to estimate the variance-covariance matrix of the within-subject repeated measures (i.e., model within-subject errors). The variance-covariance matrix will be estimated across both treatment arms. The fixed effects will be estimated by the method of restricted maximum likelihood estimation using the Newton-Raphson algorithm, based on all available data. The denominator degrees of freedom and adjustment of standard errors will use the Kenward-Roger method.

Assignment of SIGH-D-17 assessments to Visit for primary MMRM analysis:

Day 7-20 SIGH-D-17 => Week 2 Visit Day 21-34 SIGH-D-17 => Week 4 Visit Day 35-48 SIGH-D-17 => Week 6 Visit Day 49-70 SIGH-D-17 => Week 8 Visit

If the final SIGH-D-17 assessment is on Day 1-6, this SIGH-D-17 value will be assigned to the Week 2 Visit. If multiple SIGH-D-17 assessments fall within a Visit assignment range, the assessment closest in time to the nominal visit day will be retained. For example, the in range assessment taken closest to Day 14 for Week 2 Visit, will be retained.

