AGT and TAU mean change in SIGH-D-17 at Week 8 will be estimated and tested utilizing the least squares (LS) means from the treatment x visit interaction in the MMRM model. The primary analysis will test the difference (contrast) between the Week 8 LS means, at two-sided significance 0.05. The test p-value and the 95% CI for the difference in Week 8 means will be presented. Comparisons between the AGT and TAU means at Week 2, Week 4 and Week 6 will also be generated. Diagnostics for outliers, non-normality and other model assumptions will be run. Findings will be followed up with sensitivity analyses, as appropriate.

To allow comparison with previous SIGH-D-17 studies, two supportive analyses of the primary endpoint will be produced. Each will be an Analysis of Covariance (ANCOVA):

1) Last Observation Carried Forward (LOCF) analysis, and

2) Observed Cases (OC) analysis.

Each ANCOVA will include baseline SIGH-D-17, Investigative Site and Treatment Group as the independent variables in the model. The dependent variable for the LOCF analysis will be last available SIGH-D-17 change from baseline. The dependent variable for the OC analysis will be the Week 8 SIGH-D-17 score, with no imputation of missing Week 8 scores.

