The three studies are consistent with one another. The small pilot studies show evidence of efficacy, but are too small for reliable inference. Study 1 greatest observed efficacy (Cohen's d =0.58). The second pilot study (Study 3), is more rigorous, adding randomization and rater/subject blinding, with extrapolated Cohen's d = 0.47, not statistically significant.

The largest study (Study 2) shows a somewhat lower Cohen's d (0.43), a more reliable result due to the much larger sample size and the added sensitivity analyses to assess robustness. Accepting that there remains potential bias due to the non-randomized, open design, this study result was used as the best available basis for sample size calculation.

The sample size is calculated for the two-sided alpha=0.05, 90% power test of two independent means of improvement in SIGH-D-17. In this case the sample size depends only on the postulated Cohen's d, and the % dropouts. Note this should be a conservative estimation of sample size, as the actual analysis will use a more efficient MMRM method. However, this conservatism is balanced by the potential underestimation of needed sample size due to design bias in the reference study.

Using the Trial 2 observed difference in SIGH-D-17 improvement and variability, with resulting Cohen's d=0.43, the resulting sample size is 115 per group, with no dropouts. If we assume the dropout rate somewhat less than the reference (23% vs 27% reference), then with the conventional dropout correction, the needed sample size per group is 150, or 300 total randomized subjects. The table below summarizes the design properties of this size study, under varying assumptions for delta, power and % missing Week 8 SIGH-D-17 assessment. The statistical testing significance level is two-sided alpha < 0.05, and the SD is assumed to be the same (7.2).

Total Sample Size	Subject SD	Delta	Power	% Missing Week 8
300	7.2	3.09	90%	23%
300	7.2	2.67	80%	23%
300	7.2	2.94	90%	15%
300	7.2	2.54	80%	15%
300	7.2	2.85	90%	10%
300	7.2	2.46	80%	10%
300	7.2	2.70	90%	0%
300	7.2	2.34	80%	0%

Detectible\* Delta for Varying Power and Missing Data Assumptions

\*Detectible delta is the smallest postulated "true" difference between means for which 80% (or 90%) of trials would be statistically significant with the given % missing Week 8 data.

All sample size calculations used Stata Version 13 software.

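### The primary MMRM fits one baseline slope to all four visits; a baseline × visit term would protect Week 8 precision at almost no cost

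*SAP*

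**What the plan says.** SAP 3.4 (Primary Endpoint Analyses) sets out the repeated-measures model. On the outcome: "the dependent variable is the change in SIGH-D-17 from baseline at each of the scheduled visits". On the covariates: "The model will include the fixed effect continuous factor baseline SIGH-D-17, and fixed effect categorical factors investigative site, treatment group", followed by "visit (Weeks 2, 4, 6 and 8; 4 levels), and treatment x visit interaction". On the covariance: "An unstructured covariance pattern will be used to estimate the variance-covariance matrix of the within-subject repeated measures". On the test: "The primary analysis will test the difference (contrast) between the Week 8 LS means, at two-sided significance 0.05".

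Protocol 9.4.1 specifies the same terms: "The model will include the fixed effect continuous factor baseline SIGH-D-17, and fixed effect categorical factors (pooled) investigative site", with treatment, visit and treatment × visit. The Protocol Summary repeats them. The Key Secondary sections of both documents reuse this model for the continuous secondary endpoints.

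Neither document adds a baseline × visit term or gives a reason for holding the baseline slope constant over visits.

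**The concern.** The model lets the treatment effect vary by visit and leaves the covariance unstructured, but it ties the baseline slope to one value. If a subject's score depends less on baseline as the weeks pass, the slope of change on baseline becomes steeper, and no single value fits all visits. Generalised least squares gives most weight to the visits with the smallest variance, which are usually the early ones. Week 8 is then under-adjusted for baseline and its residual variance is larger than it need be.

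What is at stake is a little precision in the deciding contrast. The same slope also contributes to the Week 8 information that the model implies for subjects who leave early, so unequal dropout between the arms deserves a look.

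**Working it through.** **1. The plan's own figure.** SAP section 4 says: "The sample size is calculated for the two-sided alpha=0.05, 90% power test of two independent means of improvement in SIGH-D-17". Inputs there are delta 3.1, SD 7.2 and 23% dropout. With the noncentral t, 114 per group gives power 0.899 and 115 gives 0.902, so 115 is reproduced. Then 115 / (1 − 0.23) = 149.4, rounded up to 150 per group, 300 in total. This is an unadjusted two-sample calculation. It counts no gain from baseline adjustment, so the point does not change it.

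**2. Common slope.** Let b be the vector of true slopes of change on baseline at the four visits, Σ the residual covariance, sx the baseline SD and **1** a vector of ones. Under an unstructured covariance the fitted common slope tends to

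b* = (1′M⁻¹b) / (1′M⁻¹1), with M = Σ + sx²(b − b*)(b − b*)′.

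With complete data, the Week 8 contrast variance relative to visit-specific slopes is

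1 + (b8 − b*)² sx² / Σ88.

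**3. Inputs, all assumed (none is in the documents).** Baseline SD 3.28 (entry requires a score of 18 or more, which restricts the range); residual SDs 5.0, 6.0, 6.7 and 7.0 at Weeks 2, 4, 6 and 8, so Σ88 = 49; slopes linear between the Week 2 and Week 8 values shown.

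| Slope, Week 2 → Week 8 | Correlation | b* | Week 8 variance inflation |
|---|---|---|---|
| equal at all visits | any | = b8 | 0% |
| −0.1 → −0.3 | AR(1) 0.6 | −0.162 | 0.138² × 3.28² / 49 = 0.4% |
| −0.2 → −0.7 | AR(1) 0.6 | −0.356 | 0.344² × 3.28² / 49 = 2.6% |
| −0.1 → −0.3 | compound symmetry 0.8 | −0.060 | 0.240² × 3.28² / 49 = 1.3% |
| −0.2 → −0.7 | compound symmetry 0.8 | −0.101 | 0.599² × 3.28² / 49 = 7.9% |

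In subjects, 300 × (1 − 1/1.004) ≈ 1, 300 × (1 − 1/1.026) ≈ 8 and 300 × (1 − 1/1.079) ≈ 22. The correlation matters as much as the slopes.

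**4. A second, wider set of assumptions.** Here the regression of the visit score on baseline falls from Week 2 to Week 8 by 0.75→0.55 (mild), 0.80→0.40 (moderate) or 0.90→0.20 (strong), with baseline SD 2.5–4.5 and residual correlation 0.6–0.8. Inflation is 0.3–1.7%, 1.1–6.4% and 3.4–17.8% respectively. In the moderate case with baseline SD 3.5 and SD 7.2, b* is −0.24 to −0.31 against a Week 8 slope of −0.60. Inflation is then 2–3%, and power at delta 3.1 is 0.920–0.923 instead of 0.928.

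**5. Validity.** Both models were simulated with 300 subjects and missing-at-random dropout (23–27% missing at Week 8; 600–1,500 replicates; maximum likelihood, no site term, no Kenward-Roger).

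- Type I error of the common-slope model was 0.047 with similar dropout in the arms and 0.053 with strongly unequal dropout. Both are within simulation error of 0.05.
- With similar dropout the contrast was essentially unbiased.
- With dropout about as unequal as the 37% versus 18% that SAP section 4 reports for the reference study, the common-slope estimate at delta 3.1 was closer to zero than the interaction model's: 3.056 − 2.999 ≈ 0.06 points (moderate, baseline SD 3.5) and 3.095 − 2.957 ≈ 0.14 points (strong, baseline SD 4.5). Under no effect, the strong case differed by 0.179 − 0.010 ≈ 0.17 points.

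**The case against.** The strongest reply is that this is a modelling preference. A main-effect baseline term is a legitimate pre-specified adjustment, and the documents contain no by-visit slopes, baseline SD or inter-visit correlations. A reader might infer that Week 8 is in fact adjusted with the wrong slope. The documents do not support that: if the slopes are equal, nothing is lost. This part of the reply stands, and the point is conditional.

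A reader might also infer that dropouts' Week 8 values are mispredicted and the result biased. That does not follow either. Their observed post-baseline scores also inform the fit through the unstructured covariance, and the FAS requires at least one such score. Dropout related to severity to the same degree in both arms need not bias the contrast. Bias appeared only under strongly unequal dropout, with rates borrowed from a non-randomised, open study.

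There are partial safeguards too. SAP 3.4 plans diagnostics of model assumptions with follow-up, and the observed-cases ANCOVA estimates its own Week 8 baseline slope. However, the diagnostics do not name this check, and the ANCOVA uses only subjects seen at Week 8. They soften the point without replacing the term.

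Finally, altering a primary model after unblinding would do more harm than the loss described here. That also stands, and it shapes the fix.

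**Conclusion.** The omission is plain in both documents and unexplained, and including the term would be a minor improvement. Under the inputs in step 3, Week 8 variance inflation is 0% with equal slopes, about 0.4–2.6% with AR(1) correlation 0.6, and up to about 8% with compound symmetry 0.8. Larger figures need the strong slope change in step 4. Every non-zero figure rests on assumed slopes, SDs and correlations.

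Two stronger conclusions should not be drawn. The trial is not shown to be underpowered: 115, 150 and 300 reproduce without any credit for adjustment, so an imperfect slope gives up part of an uncounted gain. The primary test is not shown to be invalid either: the estimand is unchanged, simulated type I error stayed near 0.05, and bias arose only with differential dropout and was small.

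**What to change.** The right step depends on whether the main study is still blinded, which the documents do not settle. SAP 1.1 says version 3.0 was approved before main-study unblinding and that version 4.0 leaves the main-study analyses unchanged. Protocol 8.1 requires SAP amendments to be completed before unblinding.

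- **If still blinded:** by SAP amendment, with Protocol 9.4.1 aligned, add baseline SIGH-D-17 × visit to the primary MMRM. Add each scale's own baseline × visit to the continuous secondary MMRMs.
- **If already unblinded:** keep the pre-specified primary model. Report the interaction model as a labelled sensitivity analysis, described in the clinical study report as Protocol 8.1 provides.

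The cost is 3 extra parameters per model, negligible with about 230 (300 × 0.77 = 231) to 300 subjects. If the slopes turn out equal, almost nothing is lost. The sample size need not change, and the elderly study's LOCF ANCOVA, which has no visit term, is unaffected.

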### **Missing Data**

The MMRM analysis may be biased unless the missing SIGH-D-17 visit data are Missing at Random (MAR). This is because the MMRM, as well as LOCF and OC ANCOVA analyses assume the unobserved missing data has the same behavior as the observed data for the same treatment group and covariates. [For example, if a computer failure causes loss of some Week 8 SIGH-D-17 scores, this missing data should be MAR: the missing data is not informative about the actual Week 8 SIGH-D-17

scores, and the missing scores may be predicted from available SIGH-D-17 scores. Contrarily, if scores are missing due to subject dropout resulting from , (un-measured) worsening depression, then these missing scores would likely be Not Missing at Random (NMAR)].

To address this issue, if there is more than 10% missing Week 8 SIGH-D-17 scores, sensitivity analyses using alternate approaches to handling missing data will be explored. The sensitivity analyses will incorporate a range of plausible NMAR assumptions. As methods for NMAR sensitivity analyses are currently evolving, further technical detail will be given in a later amendment to the SAP.

#### Subgroup Analyses

Consistency of AGT vs TAU treatment effect on SIGH-D-17 will be assessed across various subgroup factors described below, by evaluating the treatment by subgroup interaction in the MMRM model. If there is evidence of inconsistency of treatment effect (i.e., p-value <0.10 for interaction test), further analyses may be performed. LS Mean Differences for each subgroup factor will be graphically displayed.

Subgroup factor	Subgroup categorization		
Age group	< median age, $\geq$ median age		
Gender	Male, Female		
Race	White, Non-white		
Baseline SIGH-D-17*	< 24, ≥ 24 (Moderate, Severe MDD)		
Previous failed drug treatments	1, >1 Previous failed, adequate trials of antidepressants in the current depressive episode		
Investigative Site	Pooled sites.		

\*The continuous baseline SIGH-D-17 term will not be in the MMRM model.

Graphical presentations of the primary efficacy subgroup results will also be provided

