4 SUBJECT ELIGIBILITY

4.1 Inclusion Criteria

The following are requirements for entry into the study:

- 1. Main Study: Age 18-75 years.
 - Exploratory Elderly MDD Study: Age \geq 65 years (enrolled under Protocol Amendment 2, v12Aug16)
- 2. Ability to understand and provide informed consent
- 3. Ability to understand, read and speak English
- Primary diagnosis of Major Depressive Disorder (without psychosis) based on DSM-5 criteria and MINI 7.0
- 5. SIGH-D-17 score ≥18 (i.e., moderate depression) at Screening and Baseline
- 6. Failure of at least 1 prior adequate trial of standard antidepressant in the current major depressive episode (using ATRQ criteria i.e., 6 weeks at adequate dose) due to inefficacy, side effects or intolerability
- 7. Subject is willing to follow study instructions, complete study assessments and likely to complete all required visits

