## Efficacy Analyses for Exploratory Elderly MDD Study

#### Primary Analysis

The Exploratory Elderly MDD Study primary analysis will test the Difference at Week 8 in mean SIGH-D-17 change from baseline in a Last Observation Carried Forward ANCOVA, adjusting for baseline SIGH-D-17 and pooled site, in the FAS set. Descriptive statistics and confidence intervals will also be calculated. The Treatment x Pooled Site and Treatment x Baseline SIGH-D-17 interaction tests, as well as diagnostics for outliers, non-normality and other model assumptions will be run, and followed up, as appropriate.

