#### Subgroup Analyses

Consistency of AGT vs TAU treatment effect on SIGH-D-17 will be assessed across subgroup factors described below, by evaluating the treatment by subgroup interaction in the LOCF ANCOVA model. If there is evidence of inconsistency of treatment effect (i.e., p-value <0.10 for interaction test), further analyses may be performed. Subgroups will include Gender, Baseline SIGH-D-17 (categorized as in the Main Study, continuous baseline SIGH-D-17 not in the model) and Pooled Site. Confidence intervals for the TAU minus AGT LS Mean Differences for each subgroup factor will be graphically displayed.

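### Main Study severity is tested as an effect modifier only through a split at SIGH-D-17 24; a continuous treatment x baseline test should be added and the continuous covariate kept in both studies' severity models

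*SAP*

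**What the plan says.** The primary MMRM adjusts for baseline as a continuous covariate: "The model will include the fixed effect continuous factor baseline SIGH-D-17" (SAP 3.4, Primary Endpoint Analyses). Subgroup consistency is then assessed "by evaluating the treatment by subgroup interaction in the MMRM model", with follow-up analyses optional when there is a "p-value <0.10 for interaction test". Baseline severity enters as two categories, below 24 and 24 or above, labelled moderate and severe. An asterisk on that row alone leads to the footnote "The continuous baseline SIGH-D-17 term will not be in the MMRM model". The other subgroup rows carry no such exception.

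The Elderly study's subgroup paragraph repeats the choice within its LOCF ANCOVA: "categorized as in the Main Study, continuous baseline SIGH-D-17 not in the model". Its primary-analysis paragraph, however, also lists "The Treatment x Pooled Site and Treatment x Baseline SIGH-D-17 interaction tests". Baseline is a covariate in that ANCOVA, so I read this as a test on the continuous score. The Main Study text has no counterpart.

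The baseline range is bounded below by the entry criterion "SIGH-D-17 score ≥18 (i.e., moderate depression) at Screening and Baseline" (Protocol 4.1). Neither document gives an expected baseline mean, SD or proportion at 24 or above.

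**The concern.** Severity is an obvious candidate effect modifier in a depression trial, and the plan makes further work on heterogeneity depend on the interaction p-value. Two separate choices bear on that p-value.

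- **The split.** Cutting the score at 24 discards the variation within each half. If the benefit of assay guidance changes gradually with severity, a two-category test detects this less often than a test on the score itself.
- **The footnote.** Removing the continuous score leaves baseline differences within each severity stratum unadjusted.

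The SAP gives no reason for the removal. The likely motive is collinearity between the score and its own category, but that affects the category main effect and hardly touches the treatment by category term. At stake is the sensitivity of one exploratory analysis. No primary or secondary test depends on it.

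**Working it through.** **The plan's own figure.** The documents quantify nothing for this subgroup. The sample size that supplies the SD does reproduce. With delta 3.1, SD 7.2, two-sided 0.05 and 90% power, n = 2 x (1.960 + 1.282)² x (7.2/3.1)² = 113.4, so 114 per group by the normal approximation and 115 by the noncentral t. Then 115/0.77 = 149.4, so 150 per group, as stated.

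**Step 1: information kept by the split.** Under 1:1 randomisation and linear modification, the fraction of interaction information kept is the squared correlation between the score and the indicator of 24 or above:

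k = q(1 − q)d²/σ²

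Here q is the proportion at 24 or above, d the difference in mean baseline between the two groups, and σ the baseline SD. A normal score split at its median gives 2/π = 0.637.

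For this trial I assume rounded normal scores truncated at 18. For location 22 and SD 4 before truncation, q = 0.407, d = 5.47 and σ = 3.27, so k = 0.407 x 0.593 x 5.47²/3.27² ≈ 0.68. Over a grid of locations 14 to 26 and SDs 3 to 5:

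| Share at 24 or above | k | Loss |
|---|---|---|
| 25% to 60% | 0.62 to 0.68 | 32% to 38% |
| 15% | 0.54 to 0.58 | 42% to 46% |
| 72% to 80% | 0.49 to 0.54 | 46% to 51% |
| 6% or less | 0.38 or less | 62% or more |

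In the central band the continuous test has 1/0.68 = 1.47 to 1/0.62 = 1.61 times the information. If the effect truly steps at 24, the split loses nothing.

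**Step 2: what that means for power.** Illustrative assumptions: 270 analysed (10% dropout), SD 7.2, a slope of 0.5 points of treatment effect per baseline point, baseline-change correlation 0.3, alpha 0.10. At location 22, SD 4:

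- SE of the interaction slope = 2 x 7.2 x √(1 − 0.09)/(√270 x 3.27) = 0.256.
- Continuous test: z = 0.5/0.256 = 1.96, power Φ(1.96 − 1.645) ≈ 0.62.
- Split: z ≈ 1.96 x √0.676 = 1.61, power ≈ 0.49.

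Simulation of this case (2,000 single-visit trials) gave 0.62 and 0.46; the split there is fitted without the covariate, which costs slightly more. Across locations 20, 22 and 24, power was 0.53 to 0.68 continuous and 0.40 to 0.51 split.

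**Step 3: the footnote on its own.** The split is kept, and the continuous covariate is either in or out. I assume the category stays as a main effect, which the SAP does not spell out. With baseline-change correlation r, residual variance is proportional to 1 − r²k without the covariate and 1 − r² with it. Adding the covariate multiplies the design variance of the treatment by category term by about 1.005 (simulated, N = 270), so

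SE ratio = √[(1 − r²k)/(1.005(1 − r²))]

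With k = 0.676:

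- r = 0.2: √(0.9730/0.9648) = 1.004
- r = 0.3: √(0.9392/0.9146) = 1.013
- r = 0.5: √(0.8310/0.7538) = 1.050

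Simulated SEs agree: 1.736 against 1.713 at r = 0.3 (1.3%), and 1.630 against 1.552 at r = 0.5 (5.0%). At the low end of the central band (k = 0.62) the r = 0.5 figure is just under 6%.

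Adding the covariate does raise the design variance of the category main effect, by a factor of about 2.1 with TAU as reference. That is where the collinearity lies, but it is not the term tested.

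**The case against.** **The one-third loss does not come from the footnote.** A reader might attach it to the removal of the covariate. The loss comes from categorising at 24. Deleting the footnote while still testing only the split would recover almost none of it; only the added continuous test does. This objection stands, and it is why the two parts are kept apart here.

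**Baseline adjustment is not abandoned.** A reader might infer that it is. If the two-level factor stays as a main effect, it carries the same 62% to 68% of the linear baseline signal in the central band. Only within-stratum adjustment is lost, and the cost is small.

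**The severity row can still be read beside the other rows.** It is tempting to call it non-comparable because its adjustment set differs. With randomised treatment and a linear model, covariate adjustment changes precision and not the treatment difference being estimated. All rows remain SIGH-D-17 mean differences.

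**The choice is conventional.** The stated aim is consistency across clinical categories, age is also split, and replacing a score by its category is common. Keeping the covariate would also put arm-level LS means for both strata at one overall baseline value. All of this is true, but the treatment differences the SAP plans to plot are unaffected, and convention does not restore the lost sensitivity.

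**It may be covered elsewhere.** The Main Study plans general model diagnostics with follow-up. The Elderly text lists its interaction tests in addition to the same diagnostics, so the SAP treats them as separate items. The route to further analyses after a p-value below 0.10 depends on the less sensitive test.

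**It may be too late to prespecify.** SAP 1.1 says Version 3.0 was signed before Main Study unblinding and that Version 4.0 leaves the Main Study analyses unchanged. The documents do not date the unblinding. If it has happened, the added test is post hoc. That limits its standing, not its usefulness.

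**Conclusion.** The point holds as a minor, low-cost improvement. Under roughly linear modification, with 25% to 60% of subjects at 24 or above, the Main Study severity test uses about 62% to 68% of the information available to a continuous interaction test. In the illustration this costs roughly 13 to 17 percentage points of power at alpha 0.10. The loss is generally larger when 24 is off-centre and nil for a true step at 24.

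The footnote and its Elderly counterpart add a separate cost of about 0.4% to 5% in the interaction standard error at correlations of 0.2 to 0.5, with no offsetting gain for the tested term.

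These sizes rest on an assumed baseline distribution, an assumed slope and correlation, and single-visit calculations in place of the MMRM. None of those inputs is in the documents apart from the SD of 7.2, the 10% dropout target and the entry floor of 18.

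**What to change.** 1. In the Main Study, make the Week 8 treatment by continuous baseline SIGH-D-17 interaction the severity consistency test, matching the test already listed for the Elderly study. In the MMRM this means letting the baseline slope and its interaction with treatment vary by visit in that exploratory model, and testing the Week 8 term.
2. Keep the LS mean differences below 24 and at 24 or above for display.
3. Delete the Main Study footnote, and the clause in the Elderly subgroup parenthesis that excludes continuous baseline (the words on categorisation can stay), so that both severity models retain the covariate. State that the category main effect is included.

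The cost is two short deletions and one extra exploratory test, with no new data and no change to the primary analysis. If the Main Study is already unblinded, label the added test post hoc and describe it in the CSR Statistical Methods section, as Protocol 8.1 provides for revisions after unblinding. The Elderly change can be made prospectively if that database is still blinded.
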